Data Management (Database)	[REDACTED] ZKS Leipzig [name] [contact]-[REDACTED] E-Mail: [REDACTED] [contact]
Data Management (Project assistance)	[REDACTED] ZKS Leipzig [name] [contact]-[REDACTED] E-Mail: [REDACTED] [contact]
Monitoring	[REDACTED] ZKS Leipzig [name] [contact]-[REDACTED] E-Mail: [REDACTED] [contact]

	                          
Steering Committee	             
DaGrader in CoRaLa II Reading Center	[name]. [name]. Department of Ophthalmology Justus-Liebig-Universität [name] [contact] E-Mail: [contact] [contact]

Synopsis

Title of the trial	Long-term need of ranibizumab injections with or without early targeted peripheral laser photocoagulation for treatment of macular edema due to central retinal vein occlusion
Acronym	CoRaLa II trial (Combination of Ranibizumab and Laser)
Indication	Macular edema due to central retinal vein occlusion
Primary goal of the trial / primary end point	
The primary objective is to evaluate whether or not the duration of guideline-conform [1] periodic ranibizumab injections may be shortened or even be successfully terminated in patient with macular edema due to central retinal vein occlusion if early targeted peripheral laser photocoagulation is applied in parallel.
 
Primary efficacy endpoint is the time to treatment success, defined as time from randomisation until the date of last criteria-based intravitreal injection in case that thereafter a treatment-free period for (at least) 6 months was observed.

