Therapy	Intravitreal injections of Ranibizumab will be applied in all patients according to treatment guidelines [1]. The experimental group will receive additional targeted laser photocoagulation of the peripheral areas of capillary non-perfusion (up to 4 laser treatments within 1st year of the study). No further additional treatments of the study eye will be given in any of the arms of the trial.
Biometry	
Analysis of the primary endpoint (within the FAS) will follow the intent-to treat principle and will be based on COX regression with the stratification factor baseline BCVA (\leq 55 letters vs $>$ 55 letters) as fixed covariate as confirmatory analysis.
 
Further models will include potentially prognostic factors and compliance for sensitivity reasons. The assumption of proportional hazard may be justified although no similar data are available by now. It will be checked and otherwise adequately dealt with. Kaplan-Meier curves provide time without treatment success per arm.
 
The number of ranibizumab injections required after the initial three injections will be analysed by linear regression model including treatment as factor with the stratification factor baseline BCVA as covariate; for sensitivity reasons, further models may include the same prognostic factors of potential relevance as selected for analyses of the primary endpoint.

Trial Duration	
First patient in to last patient out (months): 59
 
Duration of the entire trial (months): 72
 
Recruitment period (months): 30
 
Treatment period (months per patient): 23 and 6 months follow-up

Synopse (German version)

Titel der Studie	Langzeitbedarf von Ranibizumab-Injektionen mit oder ohne frühzeitige gezielte periphere Laser-Photokoagulation zur Behandlung des Makulaödems infolge eines Zentralvenenverschlusses
Kurzbezeichnung der Studie	CoRaLa II (Combination of Ranibizumab and Laser)
Indikation	Makulaödem infolge eines Zentralvenenverschlusses
Primäres Ziel der Studie/ primärer Endpunkt	
Das primäre Ziel ist die Beurteilung, ob die Dauer der Leitlinienkonformen periodischen Ranibizumab-Injektionen bei Patienten mit Makulaödem aufgrund eines Zentralvenenverschlusses verkürzt oder sogar erfolgreich beendet werden kann, wenn parallel dazu eine frühzeitige, gezielte periphere Laser-Photokoagulation durchgeführt wird.
 
Der primäre Endpunkt ist die Zeit bis zum Behandlungserfolg, definiert als die Zeit ab Randomisation bis zur letzten kriterienbasiert

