	vorgenommenen Injektion, vorausgesetzt, der Patient wies anschließend mindestens 6 Monate lang keinen erneuten Re-Injektionsbedarf (gemäß den Behandlungsrichtlinien) auf.
Sekundäre Ziele der Studie/ sekundäre Endpunkte	
Sekundäre Ziele sind die Untersuchung der Sehschärfe während und nach der Behandlungszeit, Auswirkungen auf die Lebensqualität und die Erfassung von möglichen Problemen, die möglicherweise in Zusammenhang mit der Studientherapie stehen. Sekundäre Ziele sind:
 
 • die bestkorrigierte Sehschärfe • die zentralen Netzhautdicke, gemessen mit optischer Kohärenz tomografie • die Anzahl an benötigten Ranibizumab-Injektionen bis zum Therapieerfolg, sowie bis Studienende 
Ergänzende Messgrößen von Interesse sind:
 
 • Anteil der Patienten mit Entwicklung von neovaskulären Komplikationen über die gesamte Beobachtungszeit hinweg • Gesundheitsbezogene Lebensqualität (HrQoL) • ischämische Netzhautareale • Kapillarendichte und Größe der zentralen avaskulären Zone • Möglicher Verlust des Gesichtsfeldes • Entwicklung von Kollateralen • Anzahl Laserbehandlungen und verabreichte Laserstrahlung im experimentellen Arm (RL-Arm)
Studiendesign	Multizentrische, prospektive, randomisiert, interventionelle, klinische Studie mit zwei parallelen Gruppen, Phase IIIb
Studienpopulation	
Einschlusskriterien
 
Alle folgenden Einschlusskriterien müssen erfüllt werden:
 
 1. Gesichertes Makulaödem als Folge eines Zentralvenenverschlusses. Zentrale Netzhautdicke > 250 µm (mittels OCT bestimmt). 2. Alter \geq 18 Jahre 3. Schriftliche Zustimmung der Teilnahme an der Studie 4. Sehschärfe am Studienauge zwischen 24 Buchstaben (20/320) und 78 Buchstaben (20/25) – gemessen mittels ETDRS Prüftafel 5. Zentralvenenverschluss nicht älter als 6 Monate 6. Angiographisch gesicherte periphere ischämische Netzhautareale mit einer Größe von > 5 Papillenflächen (mittels Weitwinkel-FAG) 7. Bereitschaft und Fähigkeit die vorgeschriebenen Studienvisiten einzuhalten 
Ausschlusskriterien
 
Es erfolgt kein Studieneinschluss, wenn eines der folgenden Ausschlusskriterien erfüllt ist:
 
 1. Ischämischer Zentralvenenverschluss definiert durch Vorhandensein von ischämischen Netzhautareale in der

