6.3 Description of the Treatment Procedures

Intravitreal injections of Ranibizumab will be applied in all patients according to treatment guidelines. The experimental group will receive an additional targeted laser photocoagulation of the peripheral areas of capillary non-perfusion (up to 4 laser treatments within 1st year of the study). No further additional treatments of the study eye will be given in any of the arms of the trial.

Intervention scheme of CoRaLa II Trial

* complementary endpoints in all patients at month 24.

** secondary endpoints in patients with success at that visit when success is stated; in patients without treatment success prior to visit 24, secondary endpoints will be assessed at month 29; if a patient needs treatment after success, this treatment is no longer a study treatment and therefore no further AE/SAE documentation is needed.

Based on the results of optical coherence tomography (OCT) the **diagnosis of ME** will be established and Ranibizumab injections will be indicated.

Pre-defined re-treatment criteria will be applied according to treatment guidelines in order to identify a further need of re-injections at the monthly visits.

Re-treatment with Ranibizumab is needed if the following criteria are met:

- persisting ME or
- recurrence of ME

defined as presence of intra-/sub-retinal fluid and /or central subfield thickness (**CST**) of **≥250 µm** assessed by OCT

Re-treatment criteria for laser photocoagulation: new areas of capillary non-perfusion detected with fundus photography and FA at 3 and 9 months after randomisation. Experienced graders of the CoRaLa II Central Reading Center will evaluate all fundus and FA images taken with the Zeiss 700 device and define the non-perfused retinal areas for laser photocoagulation. Laser photocoagulation will be performed at Month 2 and if needed at Months 4, 6 and 10.

Parameters needed for end-point evaluations:

- Only if no ME can be identified by OCT over 6 months of follow-up **treatment success** is stated and the time until this visit will be used in confirmatory analysis.

- **The number of Ranibizumab injections** depends on the valid assessment of presence/ or absence of ME in all monthly visits and will be counted until defined success (if applicable) and at the end of study.

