9.2 End Points

9.2.1 Primary End Point

Primary efficacy endpoint is the time to treatment success, defined as time from randomisation until the date of last criteria-based intravitreal injection in case that thereafter a treatment-free period for (at least) 6 months was observed.

Objective criteria for further treatment indication (according to details in section 6.3) have to be fulfilled for decisions regarding further re-treatment.

Drop-outs/deaths without earlier success will be censored at the end of their observation time and all other patients without documented success at month 24 or 29 after randomisation (in case of no treatment indication at the last regular visit to state or deny a late success).

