9.4 Sample Size Discussion

Long-term review of CoRaLa I [10] patients (as reported in 1.2) showed that a proportion of $p_{R\text{-only}}=0.58$ had to be treated longer than 2 years, while for all but one patient ($p_{RL}=0.1$) the combined therapy could be terminated after median [quartiles] of 10 [3;11] months but total observation times of 18 [16; 20] months.

Assuming 2 years to treatment success, rates of 50% with R-only and (conservative) 20% with RL, setting a two-sided significance level α at 5%, and requiring 90% power we need a total of $N=92$ cases with a log rank test.

With regard to the number of injections applied within two years (without the three initial monthly injections), we observed 5.6 (4.9) injections (mean (SD)) in the R-only, but 2.8 (2.7) in the RL-group. Based on these means (SD), we need $n=46$ patients per group with an α level of 5% (2-sided) and for a power of 90%.

Non-compliance and dropout rates are expected to be rather low with regard to the massive impact of impaired visual acuity on activities of daily and social living. Regarding the CoRaLa I patients one participant (of 22) was lost (after 15 months) and 2 per arm died after long-term observation of more than 4 years. Although (extended) oversampling is not needed with regard to the confirmatory analysis within the FAS and a time-to-event primary endpoint, a major interest of the trial focuses on mid-/long-term differences between the treatments, too. Therefore, we amply plan with 20% dropouts and intend to include at least 110 patients to learn as much as possible on the effect of the additional laser treatment on the further need of regular Ranibizumab injections in long-term and ensure sufficiently precise estimations after two year of observation.

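### Section 6.3 ends the confirmatory event time at the visit where success is declared; section 9.2.1 and both synopses end it at the last injection, at least 6 months earlier

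*Protocol*

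**What the plan says.** Section 6.3, in the list of parameters needed for end-point evaluation, allows success to be declared only after 6 months of follow-up without macular edema on OCT. It then says that success "is stated and the time until this visit will be used in confirmatory analysis".

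Section 9.2.1 defines the primary endpoint as "time from randomisation until the date of last criteria-based intravitreal injection in case that thereafter a treatment-free period" of at least 6 months was observed. The English synopsis uses the same words. The German synopsis agrees: "definiert als die Zeit ab Randomisation bis zur letzten kriterienbasiert" and, continuing, "vorgenommenen Injektion, vorausgesetzt, der Patient wies anschließend mindestens 6 Monate lang" no renewed need for injection.

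Section 9.2.1 also has two censoring rules. One reads "Drop-outs/deaths without earlier success will be censored at the end of their observation time". The other covers "all other patients without documented success at month 24 or 29 after randomisation": month 29 applies if there was no treatment indication at the last regular visit, and otherwise month 24.

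Section 1.2.1 describes success in terms close to 6.3 but names no analysis time. No passage reconciles the two dates.

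**The concern.** This is not a detail left to the statistical analysis plan. The protocol fixes the date of the confirmatory event twice, differently, and 6.3 names the confirmatory analysis explicitly. Section 9.2.1 sends the reader to 6.3 for the treatment criteria, so a programmer will meet both dates.

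Three things are at stake:

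- Success by month 24 and the median time to success shift by relabelling alone.
- Visit dating interacts badly with the month-24/29 censoring rule. Last injections at months 19 to 23 can be confirmed only at month 29, because no visit lies between months 24 and 29. Non-successes censored at month 24 have then left the risk set, although they are known not to have succeeded.
- If the date is not settled beforehand, it could be chosen after the data are seen.

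**Working it through.** **Inputs.** Section 9.4: 50% (R-only) and 20% (RL) without success at 2 years, two-sided 5%, 90% power, N = 92, 20% drop-out, 110 to be included. Sections 1.2.1 and 6.4: last trial injection at month 23, final visit at month 29. Assumption: exponential times to last injection.

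**The protocol's own figure.** Hazard ratio = ln 0.5 / ln 0.2 = 0.431 (inverse 2.32). Schoenfeld events = (1.960 + 1.282)² / (0.25 × (ln 0.431)²) = 59.2. Mean event probability = (0.5 + 0.8)/2 = 0.65. N = 59.2/0.65 = 91.1, or 93 from 60 events. The stated 92 is reproduced. The calculation takes the 2-year rates as given, whichever date they refer to.

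**Success by month 24.** P(last injection by month m) = 1 − S^(m/24), with S = 0.5 or 0.2.

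- Injection dating, m = 23: 1 − 0.5^(23/24) = 48.5%; 1 − 0.2^(23/24) = 78.6%.
- Visit dating, m = 18 (confirmed at month 24): 1 − 0.5^0.75 = 40.5%; 1 − 0.2^0.75 = 70.1%.
- Share of successes moved to month 29: (48.5 − 40.5)/48.5 = 16.5% in R-only and (78.6 − 70.1)/78.6 = 10.8% in RL; 13.0% overall.

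**Median.** RL: 10.3 months by injection and 16.3 by visit (11 and 17 on a monthly grid). R-only: 24.0 and 30.0, which is beyond the last possible event (month 23 or 29) on either date.

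**Share of non-successes followed to month 29.** The protocol does not give it. A rough value places the 5.6 R-only injections after loading (section 9.4) on the 50% still treated: 5.6/0.5 = 11.2 of up to 20 (section 3.1), so 56% of visits carry an indication if spread evenly, and 44% do not. The higher counts in section 1.1 would lower this.

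**Simulation.** 55 per arm, 4000 runs, the same simulated patients under both dates. Last injections lie on a monthly grid from month 3 to 23. Those at months 3 to 18 are confirmed 6 months later, those at months 19 to 23 at month 29. Cox model with Efron ties. The Monte Carlo error of power is about 0.4 to 0.6 points. Without drop-out:

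| Dating | Share followed to month 29 | HR | Power | Kaplan-Meier success at month 29, R-only / RL |
|---|---|---|---|---|
| Injection (9.2.1) | any | 2.33 | 94% | 48.5% / 78.6% (exact) |
| Visit (6.3) | 100% | 2.33 | 94% | 49% / 79% |
| Visit (6.3) | 44% | 2.30 | 93% | 56% / 84% |
| Visit (6.3) | 25% | 2.27 | 92% | 63.5% / 88.5% |
| Visit (6.3) | 10% (boundary) | 2.21 | 90% | 77% / 94% |
| Visit (6.3) | 0% (boundary) | 2.10 | 87% | 99% / 100% |

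With 20% drop-out by month 29, injection dating gives HR 2.31 and power 89%. Visit dating gives 2.30 and 89% (share 44%), 2.27 and 88% (25%), and 2.12 and 83% (0%).

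**Which date the rest of the protocol supports.** Section 9.4 plans from times at which "the combined therapy could be terminated after median [quartiles] of 10 [3;11] months"; these are end-of-treatment times. The month-24/29 rule does no harm under injection dating, where every event falls by month 23. The drop-out rule fits visit dating better. Under injection dating with 20% drop-out it gives 46.8%/76.6% success by month 24, against 48.5%/78.5% if drop-outs are censored 6 months earlier (HR 2.31 against 2.33).

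**The case against.** The strongest reply is that this is a wording slip. The formal endpoint section and both synopses agree, and the outlier is half a sentence in a treatment-procedures list. At the central share the hazard ratio moves from 2.33 to 2.30 and power from 94% to 93%. This stands for the hypothesis test. It does not cover the reported success rates and medians, or the need for one event date fixed in advance.

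The Kaplan-Meier inflation comes from combining the 6.3 date with the 9.2.1 censoring rule, not from 6.3 alone. That is true, but it is what results if both passages are followed as written.

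The 44% share is weak. With the observed 0.58 still treated beyond 2 years in place of 50%, it becomes 5.6/0.58 = 9.7, 9.7/20 = 48%, so 52%. This also stands, and is why a range is shown; the conclusion on the Cox model does not depend on the exact value.

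Bi-monthly visits in year 2 could delay confirmation. Visits 2, 4 and 6 months after the last injection still confirm at exactly 6 months, and any slip only widens the gap between the two dates.

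Finally, the month-24/29 rule does not show which date was intended, since months 24 and 29 are equivalent for the Cox model under injection dating. Agreed: the rule is compatible with injection dating and distorts only under visit dating.

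**Conclusion.** The contradiction is real and should be fixed before analysis. Section 6.3 gives the confirmatory event a date at least 6 months later than the endpoint definition. Under the planning rates and exponential times, following it lowers reported success by month 24 by about 8 percentage points in each arm and adds 6 months to the median in the laser arm.

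The sample size stands. The Cox result is nearly unchanged if at least a quarter of the non-successes are followed to month 29. It weakens noticeably only near the boundary where almost none are, and the protocol does not give that share. Kaplan-Meier estimates after month 24 are too high under visit dating unless nearly all non-successes are followed.

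**What to change.** Keep 9.2.1 as the only definition of the event. In 6.3, end the sentence where success is stated and delete the remainder about the time used in the confirmatory analysis. Add that success is confirmed at this visit but is dated, for the confirmatory analysis, at the last criteria-based injection as in 9.2.1. The success criterion in 6.3, section 1.2.1 and the sample size need no change for this.

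Optional and minor: censor drop-outs and deaths without confirmed success 6 months before their last observation, since a later event could not have been confirmed. This would need a stated rule for patients who leave before month 6 (1 − 0.8^(6/29) = 4.5%, about 5 of 110, at 20% exponential drop-out).

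The cost is one clause of wording. No new visits or data are needed: injection dates are already recorded and the month-29 visit is already mandatory for all patients.

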6.3.1 Screening visit (Day -14 to Day 0)

- Signed informed consent
- Medical history and ophthalmic history
- Assessment for women of childbearing potential: urine pregnancy test
- Blood pressure and pulse
- Ocular assessments (study eye and fellow eye):
 - Investigation of BCVA using ETDRS chart **performed by a blinded assessor**
 - IOP
 - Gonioscopy (exception: study eye only!)
 - Slit lamp biomicroscopy
 - OCT (in addition OCT will be evaluated by the CoRaLa II Central Reading Center)

- OCT-Angiography (in addition OCT-Angiography will be evaluated by the CoRaLa II Central Reading Center)
- Ophthalmoscopy
- Fundus photography and Fluorescein angiography (FAG) performed according to the imaging protocol and evaluated by the CoRaLa II Central Reading Center.

⇒ If all inclusion criteria and no exclusion criteria apply randomisation is performed.
 ⇒ **The screening visit may be performed together with Baseline Visit on the same day.**

6.3.2 Day 1 – Visit 1 (Baseline), Visit 2 (month 2 +/- 7 days) and Visit 3 (month 3 +/- 7 days)

- Blood pressure and pulse
- QoL (Visual Function Questionnaire) only at Baseline
- Documentation of Adverse events, critical ocular events and Concomitant medication
- Ocular assessment (assess prior to injection, assess in the study eye only):
 - Investigation of BCVA using ETDRS chart **performed by a blinded assessor**
 - IOP
 - Slit lamp biomicroscopy
 - OCT (in addition OCT will be evaluated by the CoRaLa II Central Reading Center)
 - Ophthalmoscopy
 - Fundus photography and Fluorescein angiography (FAG) performed according to the imaging protocol and evaluated by the CoRaLa II Central Reading Center, **only at Visit 3.**

➤ Control group:
 Ranibizumab injection at Baseline, Visit 2 and Visit 3.

➤ Experimental group:
 Ranibizumab injection at Baseline, Visit 2 and Visit 3.
ONLY at Visit 2 (Month 2) laser photocoagulation will be performed in the experimental arm before injection of Ranibizumab.

6.3.3 Visit 4 (month 4 +/- 7 days) Start of Maintenance dosing phase monthly Visits up to Visit 12 (month 12 +/- 7 days)

- Blood pressure and pulse

- QoL (Visual Function Questionnaire) only at Visit 12 before the ophthalmologic investigation will be performed
- Documentation of Adverse events, critical ocular events and Concomitant medication
- Ocular assessment (assess prior to injection, assess in the study eye only, see exceptions in text below):
 - Investigation of BCVA using ETDRS chart **performed by a blinded assessor**
 - IOP
 - Gonioscopy only at Visit 12
 - Slit lamp biomicroscopy
 - Visual field performed only at Visit 4 in both eyes
 - OCT (in addition OCT will be evaluated by the CoRaLa II Central Reading Center)
 - OCT-angiography only at Visit 4 and Visit 12 (in addition OCT-Angiography will be evaluated by the CoRaLa II Central Reading Center)
 - Ophthalmoscopy
 - Fundus photography and Fluorescein angiography (FAG) performed according to the imaging protocol and evaluated by the CoRaLa II Central Reading Center **only at Visit 9.**

Assesement of re-treatment criteria

- Control group and experimental group: if re-treatment criteria are met, then Ranibizumab injection will be performed.
- Experimental group ONLY at the Visits 4, 6 and 10 laser photocoagulation will be performed, if required.

6.3.4 Visit 13 (month 13 +/- 7 days) to Visit 23 (End of treatment) month 23 +/- 7 days

- ⇒ If patient has reached already treatment success, only the mandatory study visits (16 and 20) will be performed.
- ⇒ If patient still needs re-injections, study visits will be performed monthly.
- ⇒ Patients who are free of intravitreal treatment ≥ 2 months will be seen bi-monthly.
- ⇒ If the treatment interval is < 2 months, the patients will be followed monthly until the treatment success has been reached or treatment interval is ≥ 2 months for at least 2 consecutive injections

Nevertheless Visits 16 and 20 are mandatory for all patients to assess endpoint- relevant parameters.

- Blood pressure and pulse
- Documentation of Adverse events, critical ocular events and Concomitant medication

- Ocular assessment (assess prior to injection, assess in the study eye only):
 - Investigation of BCVA using ETDRS chart **performed by a blinded assessor**
 - IOP
 - Slit lamp biomicroscopy
 - OCT (in addition OCT will be evaluated by the CoRaLa II Central Reading Center)
 - Ophthalmoscopy
 - Fundus photography and Fluorescein angiography performed according to the imaging protocol and evaluated by the CoRaLa II Central Reading Center **only at Visit 16.**

Assessment of re-treatment criteria,

- Control group and experimental group: if re-treatment criteria are met, then Ranibizumab injection will be performed.

6.3.5 Visit 24 (month 24 +/- 7 days) is a mandatory visit for all patients

Safety visit and end of (S)AE report period (4 weeks after EoT) for patients who still need monthly intravitreal injections (no success reached).

- Blood pressure and pulse
- QoL (Visual Function Questionnaire) before the ophthalmologic investigation will be performed
- Documentation of Adverse events, critical ocular events and Concomitant medication
- Ocular assessment (assess prior to injection, assess in the study eye only, see exceptions in text below):
 - Investigation of BCVA using ETDRS chart **performed by a blinded assessor in both eyes!**
 - IOP
 - Gonioscopy
 - Slit lamp biomicroscopy
 - Visual field performed **in both eyes!**
 - OCT **in both eyes!** (in addition OCT will be evaluated by the CoRaLa II Central Reading Center)
 - OCT-Angiography **in both eyes!** (in addition OCT-Angiography will be evaluated by the CoRaLa II Central Reading Center)
 - Ophthalmoscopy performed **in both eyes!**

- Fundus photography and Fluorescein angiography (FAG) **in both eyes!** performed according to the imaging protocol and evaluated by the CoRaLa II Central Reading Center.
- Documentation if an injection with Ranibizumab was needed. (Injections of Ranibizumab after Months 23 are no longer documented as study treatment.)

6.4 Follow-up Visit 25 (month 29 +/- 7 days) **EoS** is a mandatory visit for all patients

Ocular assessment (study eye only) providing the final assessment of all secondary endpoints and any potentially late occurrence of critical ocular events.

- Blood pressure and pulse
- Critical ocular events and Concomitant medication
- Ocular assessments in study eye only:
 - Investigation of BCVA using ETDRS chart **performed by a blinded assessor**
 - IOP
 - Slit lamp biomicroscopy
 - OCT (in addition OCT will be evaluated by the CoRaLa II Central Reading Center)
 - OCT-Angiography (in addition OCT-angiography will be evaluated by the CoRaLa II Central Reading Center)
 - Ophthalmoscopy
- Documentation how many injections with Ranibizumab were needed. (Injections of Ranibizumab after Months 23 are no longer documented as study treatment.)

